4.1 Preliminary studies

Our preliminary evaluation of BPG was part of a clinical trial evaluating the effectiveness of *Captain's Log* CCRT (a "for profit" commercial CCRT game package) with HIV+ Ugandan children.⁶ We used the same configuration of Captain's Log as earlier.^{5,21} [name] and [name] reviewed each of 35 possible training tasks

with their Ugandan Co-Is and selected 9 games considered to be culturally fair. The games included 3 tasks emphasizing visual-spatial working memory, vigilance attention, and nonverbal reasoning. Using *Captain's Log* internal performance evaluation, we evaluated the static vs dynamic CCRT-related performance measures in comparison to the gold standard neuropsychological assessment battery (KABC-II, TOVA, CogState). Our severe malaria CCRT RCT results for [name] *et al* 2018 are "in press" in *Brain Research Bulletin*, available online (<https://doi.org/10.1016/j.brainresbull.2018.03.002>

Static vs Dynamic Performance Evaluation for *Captain's Log* CCRT with KABC-II MPI gains. In [name] et al, 2018, *Captain's Log* performance data for severe malaria survivors were analyzed for N=104 children (both the full and limited CCRT intervention arms) who participated in the *Captain's Log* CCRT RCT. There was a very strong (R-squared over 0.9) linear relationship between performance measures averaged.

Table 1. Concurrent validity of dynamic performance measures for 12 training sessions (N=104).

[figure not shown]
Dynamic CCRT performance assessment measures across first 12 training sessions.	Correlation with baseline (Static Pre-) MPI, p-value	Correlation with post-training (Static Post-) MPI, p-value	Coefficient (standard error) predicting post-training MPI over and above baseline (Dynamic) MPI, p-value
Mean memory success performance	r=0.32, p<.01	r=0.37, p<.01	aBeta=0.34 (0.16), p=.04
Mean probability of success performance	r=0.32, p<.01	r=0.38, p<.01	aBeta=0.27 (0.12), p=.04
Mean accuracy of memory performance	r=0.34, p<.01	r=0.41, p<.01	aBeta=0.30 (0.12), p=.01
Mean accuracy of memory processing	r=0.39, p<.01	r=0.47, p<.01	aBeta=0.35 (0.12), p<.01
Mean accuracy of visual special learning	r=0.31, p<.01	r=0.39, p<.01	aBeta=0.34 (0.13), p=.01
Slope memory success performance	r=0.24, p=.01	r=0.32, p<.01	aBeta=0.78 (0.33), p=.02

Slope probability of success performance	$r=0.28$, $p<.01$	$r=0.34$, $p<.01$	$aBeta=0.55$ (0.26), $p=0.04$
--	--------------------	--------------------	-------------------------------

side of Fig. 4 slope). Thus, dynamic measures over 12 sessions carry the same information as measures over all 24 sessions.

Table 1 shows correlations of CCRT performance gains with the KABC-II mental processing index (MPI) pre-training (Static Pre-) and post-training (Static Post-). Measures over first 12 sessions (4 weeks) had the same or stronger correlations with the KABC-II MPI, than measures based on 24 sessions (Dynamic), further confirming the adequacy of 12 sessions for dynamic measurement. To determine the value added by dynamic measures over existing static (Static Pre- or Post-) assessments, we used general linear models relating the KABC-II MPI post-training to the KABC-II MPI pre-training, and each dynamic performance measure (one at a time over each successive training session). While the KABC-II MPI at baseline was strongly associated with the KABC MPI post-training, the performance measures were significantly related to the KABC MPI post-training over and above baseline MPI (Dynamic column in Table 1), capturing variation in post-training KABC-II MPI not captured by the *Captain's Log* Static Pre- or Post- measures.

For children at each session, with consistent linear growth across all successive training sessions (Fig.4). Dynamic measures derived based on the first 12 sessions (left side of Fig. 4 slope) had the same rate of gains over time as measures across the final 12 sessions (right side of Fig. 4 slope).

(horizontal axis) as measured by CSF neuroinflammatory (TNF-alpha) and endothelial activation (von Willibrand Factor: vWF) during acute illness. The full CCRT (blue), limited CCRT (green) and control (red) arms are represented for the cerebral malaria (left side) and non-malaria (right side) cohorts. More severely affected children show poorer positive neuroplasticity in terms of CCRT learning benefit. We expect the same result for our HIV-affected cohorts, further showing the sensitivity of CCRT assessment measures.

Since the focus is on assessment as part of neurocognitive rehabilitation (CCRT), we propose that using computer games to provide for dynamic measures across 12 sessions is much more feasible, from the standpoint of disseminating BPG as an assessment and rehabilitative tool. Also, our initial pilot study with CCRT and Ugandan children with HIV had a significant gold standard test benefit across just 12 training sessions.⁵

Table 2. Results of CCTP Repeated Measures Analyses Severe Malaria Study

	Significance Level (p =)		
CCTP Score	Group	Time	GroupXTime
Memory	0.93	0.0001	0.40
Concentration	0.92	0.0001	0.58
Auditory Processing	0.41	0.0001	0.78
Visual Processing	0.74	0.0001	0.68
Problem Solving	0.99	0.0001	0.96
Self-Discipline	0.78	0.0001	0.70

Figure 5 (above right) depicts the relationship between CCRT benefit (vertical axis) and severity of illness

4.3 Research Sites

The Culture-specific neurodevelopmental assessment of HIV-affected children study will be carried out at the MU-JHU Research Collaboration clinic located at the Mulago National Referral Hospital in Kampala, Uganda. The second clinical research site is the Johns Hopkins-College of Medicine Research Project in Blantyre, Malawi which also has extensive research infra-structure. The clinical aspects of the protocol will be conducted at these two research sites along with BPG training and assessments.

The Uganda and Blantyre Malawi sites participated in the Promoting Maternal and Infant Survival Everywhere Neurodevelopment follow-up study (PROMISE ND Study) from which the Culture-specific neurodevelopmental assessment of HEU and HUU children participants will be recruited (Drs. [name] and [name] were PROMISE Co-chairs). The NIH-sponsored PROMISE 1077-BF study (NCT01061151 clinicaltrials.gov registry) from which children for the PROMISE ND study were co-enrolled, was the first Africa-based multi-site randomized clinical trial comparing the safety and efficacy of use of maternal triple ARVs to antenatal maternal ZDV alone; and postnatal maternal triple ARVs to infant NVP throughout breastfeeding. For the PROMISE ND study, a prospective cohort of HIV-exposed uninfected (HEU) children was co-enrolled from the IMPAACT/PROMISE-BF randomized clinical trial. Age-and-gender-matched controls were enrolled from child-well clinics between 09/2013-10/2014 at two sites: Blantyre, Malawi and Kampala, Uganda.

Figure 5: Flow of the PROMISE Trial and PROMISE ND Study from which we will recruit the Culture-specific neurodevelopment assessment of HIV-affected children study (HEU and HUU participants)


PROMISE Trial
 
N=3490
 
--14sites S. and E. Africa, India,
 
--Enrolled HIV+ pregnant women
 
--Antenatal Maternal ART versus
 
Mat ZDV/sd NVP
 
--Breastfeeding: Maternal ART
 
Versus infant NVP during BF
 
--March2011-Sept2106
	
PROMISE ND
 
N=738
 
--Enrolling PROMISE ND sites: Uganda, Malawi
 
--5-year cohort follow up
 
PROMISE
 
Mothers and their HEU children
 
--Age and gender-matched HUU children
 
--Evaluated neurodevelopmental outcomes in children at 12, 14, 48 and 60 months of age
 
--Enrolled2013-2014.
	
Culture-specific neurodevelopment assessment of HIV-affected children
 
N=600
 
--HEU and HUU children at 2
 
PROMISE ND sites: Malawi and Uganda
 
--Establish validity of static and dynamic measures of neurodevelopment using Brain Powered games thru' 12-sessions
 
-- 6months post-training followup
 
-- Additional training for underperforming children

--	--	---

5.0 NEURODEVELOPMENTAL ASSESSMENT PROTOCOL DESIGN

5.1 Overview of Study Design:

[figure not shown]
Static and Dynamic Assessment Process for Each Study Child. Figure 6 provides an overview of study visits and assessments. Following enrollment and physical and medical exams, each child will return to the clinic with their principal caregiver for a half-day of gold standard neuropsychological assessments (KABC-II, TOVA, CogState). At this time the caregiver will complete the Achenbach CBCL questionnaire for school-age children, the Caldwell HOME scale, the SES material possessions evaluation, and the Hopkins Symptom Checklist-25 (caregiver psychological well-being). We will explain assessments and provide instructions in the local language. Study assessments will proceed in two phases. In Phase I, children will be randomized to start BPG trainings (50% of sample) or to a wait-list condition. Within a week after baseline assessment, the full sample of children will be contacted by a field research assistant and facilitate a first BPG session. This first session will be completed by the full sample because it will be considered as an internal performance evaluation session with BPG and will be completed on a tablet, supervised by the field research assistant. This will be done as part of the 50-60 minutes training session on the 5 BPG games (about 10 minutes per game), and will constitute the BPG static assessment. Thereafter, the field research assistant will return with children allocated to the BPG trainings (50% of sample) at a convenient time and supervise BPG training several times per week until 12 training sessions are completed. The 12th session internal evaluation performance measures for the 5 core games and one added EF game will provide the endpoint for BPG dynamic assessment (gain in BPG performance from session 1 to session 12). Because BPG training will occur on a tablet connected to the internet through the mobile network, performance data can be uploaded for analysis via the MSU GEL lab principal server, as done in the Kayunga Uganda CCRT study with BPG ¹.

Post Testing and 6-month BPG Dynamic Assessment Follow-up. Within 2-4 weeks after completing BPG training and dynamic assessment, the full sample of children and their caregivers will return to the clinic for a full gold standard neuropsychological evaluation as the caregiver once again completes the CBCL. The final step in Phase I of our study process will be when the field research assistant returns with the child one final time after 6 months to administer 1 session of the BPG games to the full sample (corresponding to an internal performance evaluation for one final time). Within 2-4 weeks of this final BPG assessment, all children and their caregivers will return to the clinic for a gold standard neuropsychological evaluation. Our rationale for choosing when to have the final assessment is based on past work: after 6 months without training, the benefits of training may begin to diminish in terms of a slower rate of change in comparison to the rate of change during the training period. This BPG performance change from post training to 6-mo follow-up will provide an additional dynamic outcome for validity analyses.

In Phase 2 of the study we will assess the static and dynamic properties of an executive behavior-focused cognitive rehabilitation game package called Village Builder. In this Phase, children allocated to the wait-list condition will complete 12 sessions of training with Village Builder in a mobile device and facilitated by a research assistant. Within 2-4 weeks of the final Village Builder session, children will attend the clinic for a gold standard neuropsychological evaluation using the same battery of tests as in Phase 1. The last visit of Phase 2 will be 6 months (+/- 4 weeks) after completion of the training, where a final session of Village Builder will be administered (static evaluation) along with the battery of neuropsychological tests. Caregivers will also complete the CBCL, SES and HOME assessments in the same study visits as their children.

Figure 6. Study visits and assessments (numbers for 1 site shown)

PHASE I

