With NIH funding we previously developed BPG (Brain Powered Games), a CCRT (Computerized Cognitive Rehabilitation Therapy) digital games package for HIV+ school children in the sub-Saharan. As a child plays, BPG gathers game data that can be used for neurocognitive assessment. In this new study, we will further evaluate the capability of BPG as a test for neurodevelopment. In a second phase, we will add an award-winning game developed at the MSU-GEL lab that will train executive function (EF), allowing us to dynamically assess this often-neglected neurocognitive domain in previously tested and well-characterized HIV+, HEU and HUU cohorts of children.

In Study Aim 1 we will adapt and evaluate concurrent and predictive validity of BPG. Here we will evaluate whether BPG as a static (baseline) assessment corresponds to a gold standard of static measures (KABC-II,

TOVA, CogState). Compared to these, we hypothesize that dynamic BPG assessments will be feasible and acceptable, providing for a more sensitive evaluation of brain/behavior function as affected by more proximal factors of HIV exposure, disease and treatment. We also hypothesize that dynamic assessments will be more sensitive to distal developmental risk factors (e.g., SES, nutrition/growth, maternal caregiving quality), measured in early childhood in study cohorts.

In Study Aim 2, we will compare the validity of BPG static and dynamic assessments. Here we will validate BPG static and dynamic assessments with a gold standard of neuropsychological tests previously used with school-age children at our two study sites (Kampala, Uganda and Blantyre, Malawi). Cohorts will be well characterized due to participating in our previous NIH-sponsored HIV clinical trials. We hypothesize that BGP-based static and dynamic assessments will be sensitive to cohorts' prior longitudinal trajectories as affected by proximal and distal risk factors that cause developmental delay and cognitive problems, as measured in our previous clinical trial studies with these cohorts. The executive function game will prove especially sensitive.

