5.2 Study goals, aims and objectives

5.2.1 Study Goal

The overall goal of this research is to adapt and validate BPG as a measure to assess cognitive changes as a child plays with BPG once (static assessment) and over the course of 12 training sessions (dynamic assessments of cognitive change over time).

5.2.2 Aims and objectives:

Aim 1: To adapt and evaluate concurrent and predictive validity of BPG static (baseline) and dynamic (during 12 training sessions) cognitive assessments at the Malawi and Uganda sites.

Objective 1.1 To evaluate whether BPG static (baseline) assessment corresponds to the gold standard static measures previously adapted to HEU, HUU, and HIV+ study cohorts at Uganda and Malawi country sites (KABC-II, TOVA, CogState).

Aim 2: To compare the validity of BPG static and dynamic assessments.

Objective 2.1 To evaluate the correspondence of BGP-based static and dynamic assessments the cohorts' prior early childhood longitudinal trajectories (KABC-II), considering the effect of proximal (e.g. HIV status) & distal (height, weight, HIV disease factors, demographic) risk factors causing developmental delay and cognitive problems.

Aim 3: To test the sensitivity of dynamic assessment to learning loss over time by evaluating how much BPG performance gains diminish during a 6-month absence of training

Objective 3.1 To assess change over time in KABC-II, TOVA and CogState scores (learning loss) 6 months after the children complete 12 sessions of BPG training, overall and by cohort.

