Spatial Navigation Training (SNT; Figure 5). This is BPG's newest game, piloted in Uganda for the first time in June, 2016 with adults and also with children with HIV. SNT involves a relatively new approach to cognitive training that uses a procedure (spatial navigation) that is localized to the hippocampus, the area most involved with visual-spatial memory and learning.⁶² Spatial navigation is getting increased emphasis in computer gaming because spatial navigation training generalizes to other aspects of verbal and visual learning and memory performance. In this game the child "moves" about in a virtual maze with pictures of common African animals at intersections (Figure 5). SNT stimulates not only the hippocampus, but also other mobility-related brain areas (similar to what happens in imaging studies when a person is asked to imagine walking).¹⁴ In two recent publications, Co-I [name] and colleagues showed that after 12 sessions of SNT, older adults demonstrated improvements in both executive functioning and more complex aspects of mobility.^{15,16} SPN is presently being used by [name] and [name] in a pilot study with aging HIV adult patients in Uganda.

Village Builder (VB). [name] and his MSU-GEL team will develop a game emphasizing social cooperation (prosocial) and emphasizing reasoning and planning skills. This executive function game will use the same African village motif and animals in the existing BPG package. However, it will differ in that children will use their avatars in a cooperative manner to add dwellings to the village and domesticated animals (livestock such as goats, cattle, pigs, chickens) to the surrounding village compounds so as to increase the available resources in a positive manner.

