5.6.6 Summary of Procedures by Study visit

The following procedures will be conducted at the screening and enrollment visit of all enrollees

Table 1: Enrollment and Intake Visit(s) for all enrollees

Component	Procedures
Administrative and Regulatory	
 • Assess eligibility • Obtain written informed consent/ assent • Assign a Participant Identification (PTID) Number • Provide reimbursement for study visit
Clinical	
 • Obtain medical history • Conduct a brief physical examination (main organ systems and
Neurodevelopment Assessments	KABC-II TOVA
Caregiver-reported assessments	CBCL HOME
Brain Powered Games	1 st session for treatment condition (e.g. training) and only 1 session for wait list group (e.g. assessment)

*Depending on staff availability and scheduling, enrollment and baseline visits will be done on the same day

Table 2: BPG training visits for 50% of sample

Component	Procedures
Administrative and	
 • Schedule next visit
Brain Powered Games package	
 • Complete 10 sessions (About 2 per week for 6 weeks) of approximately 30-45 min

Table 3: Follow-up Visits for all enrollees

Component	Procedures
Administrative and	
 • Provide reimbursement for study visit

Clinical	
 • Obtain medical history • Conduct a brief physical examination (main organ systems and
Neurodevelopment Assessments	KABC-II TOVA
Caregiver-reported assessments	CBCL HOME
Brain Powered Games	12th session for BPG training group and 1 session for wait list group 1 session at 6-months follow-up for entire sample

Table 4: 12 session trainings of Village Builder (wait-list) and

Component	Procedures
Administrative and	
 • Provide reimbursement for study visit
Clinical	
 • Obtain medical history • Conduct a brief physical examination (main organ systems and
Neurodevelopment Assessments	KABC-II TOVA
Caregiver-reported assessments	CBCL HOME
Village Builder	
 • Complete 12 sessions (About 2 per week for 6 weeks) of approximately 30-45 min

Table 5: Follow-up visits for wait-list group

Component	Procedures
Administrative and	
 • Provide reimbursement for study visit

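### The Phase I dynamic endpoint counts an executive-function game with no described session-1 score, and the predictive model in Section 7.1.2 does not isolate the training gain

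*Combined protocol and SAP*

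**What the plan says.** **Games in the endpoint.** In Section 5.1, session 1 for the full sample is part of a "50-60 minutes training session on the 5 BPG games (about 10 minutes per game), and will constitute the BPG static assessment". The same paragraph then says that the session-12 "performance measures for the 5 core games and one added EF game will provide the endpoint for BPG dynamic assessment (gain in BPG performance", with the gain running from session 1 to session 12.

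**Place of the EF game.** Section 5.6.5 describes Butterfly, iSpy, Stampede, Whacky Animal and Spatial Navigation Training, and then one EF game, Village Builder: "This executive function game will use the same African village motif and animals in the existing BPG package". Section 3.0 gives its timing: "In a second phase, we will add an award-winning game developed at the MSU-GEL lab that will train executive function (EF". The Phase 2 text of Section 5.1 gives its recipients: "children allocated to the wait-list condition will complete 12 sessions of training with Village Builder". In Section 5.6.6 Village Builder appears only in Tables 4 and 5. The Table 4 heading breaks off after naming the wait-list; the Table 5 heading names only the wait-list group.

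**Analysis.** The central hypothesis in Section 2.0 is that performance gains explain variation in later gold-standard scores beyond the static assessment. The predictive model for Aims 1 and 2 in Section 7.1.2 is a mixed model for gold-standard scores at 1 and 7 months. Its covariates include BPG at intake and at 1 month, the latter labelled post-training and time-varying. Section 5.6.6, Table 3, shows what the post-training BPG score is: "12th session for BPG training group and 1 session for wait list group".

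**The concern.** There are two linked problems.

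First, a gain needs a score at both ends. The game counted at session 12 but not described at session 1 has no gain, and the sections disagree on whether Phase I children play it at all. This affects design as well as wording. Section 5.6.5 asks what the EF game adds to the existing package. If the Section 5.1 endpoint clause holds, 12-session core and EF gains belong to the same trained children. If the Phase 2 placement holds, they belong to different randomized halves.

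Second, the study exists to compare static with dynamic assessment, yet the model that should test the dynamic part does not name the gain. It treats one variable as having the same meaning in two arms where it measures different things. The analyst would have to settle, possibly after seeing data, which games form the gain and how it enters the model.

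**Working it through.** **1. Which games have a gain.** Session 1 describes five games and session 12 describes six. A session-1-to-12 gain can be formed for the five core games and not for the sixth. Section 5.6.5 lists five games plus one EF game, so the added game can only be Village Builder.

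**2. How many children.** Sections 5.4 and 5.6.1 give, per site, 60 HEU + 60 HUU + 30 HIV+ = 150 assigned to BPG training and 150 to the wait-list. Two sites give 2 × 150 = 300 in each arm. None of the 300 trained children has a described session-1 EF score. An EF gain can be formed in Phase 2 for the 300 wait-list children.

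**3. What the predictive model estimates.** Let S1 be the intake score and S12 the 1-month score.
- Entered as two terms: b1·S1 + b2·S12 = (b1 + b2)·S1 + b2·(S12 − S1). So b2 is the coefficient of the change, given the static score.
- Entered as one time-varying column: there is a single BPG coefficient and no separate term for change.

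The label in Section 7.1.2 leaves both readings open. Even on the first, S12 − S1 is training gain in one arm and change between single sessions in the other. With no arm term, b2 is one coefficient for both, and any difference between arms in 1-month BPG and gold-standard scores also feeds into it.

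**4. Can the trained half carry the analysis?** Assume an ordinary linear model with one gold-standard outcome, the static score and one added predictor, two-sided 0.05. Power comes from the noncentral F distribution with λ = n·r²/(1 − r²), where r is the partial correlation.
- n = 300, r = 0.160: λ = 300 × 0.0256/0.9744 = 7.88, power 80%.
- n = 300, r = 0.206: power 95.3%.
- n = 285 (95% retention, in line with the rate above 95% reported for earlier trials in Section 5.6.7): 80% at r = 0.164, and 94.3% at r = 0.206.

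For context, Table 1 of Section 4.1 (Captain's Log, 104 severe malaria survivors) gives coefficients and standard errors given baseline MPI. With T = coefficient/SE and 104 − 3 = 101 degrees of freedom, partial r = T/√(T² + 101). The five means give 0.207, 0.218, 0.241, 0.279 and 0.252; the two slopes give 0.229 and 0.206. No two-session gain was tested there.

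**5. Would a 12-session slope be more precise than the stated gain?** With independent errors of variance σ², the gain has error variance 2σ². The slope scaled to 11 session steps has 121σ²/143 = 0.846σ². The ratio is 2.36. With first-order autocorrelation of 0.15, 0.3, 0.5 and 0.7 it falls to 1.89, 1.52, 1.15 and 0.92. A cubic curve with independent errors gives 1.18. No advantage is established without knowing the error structure and the shape of the curve.

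**The case against.** The EF wording is one clause in a design overview, and other sections give Village Builder its own phase, sessions and follow-up. No sentence says that the EF game is withheld at session 1, and 60 minutes at about 10 minutes per game could hold six games. Section 5.6 mentions training with either or both packages, the Table 4 heading is cut off, and Figure 6 is not shown. It would therefore go too far to say that no child in the study can have both a 12-session core gain and an EF gain. That leaves the mismatch inside Section 5.1 in place.

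Wait-list children also play BPG at intake, at 1 month and at 6-month follow-up. Under the Phase 2 placement, EF scores can thus still be compared with single-session core scores within the same children; only the 12-session gains are split between arms. Sections 5.3 and 5.6.5 do state an intent to study the EF game against the gold standard. What is missing is its analysis in Section 7.1.2.

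A reader might infer that Section 7 ignores change. It does not. The standardized response mean, Guyatt's version of it and the Aim 3 time contrast all describe change, and Section 5.1 adds the follow-up change: "This BPG performance change from post training to 6-mo follow-up will provide an additional dynamic outcome for validity analyses". These summarise change; they do not test gain as a predictor beyond the static score.

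A reader might also infer that leaving sessions 2 to 11 out of the named analyses is an error, since Section 5.2 speaks of assessment "dynamic (during 12 training sessions) cognitive assessments at the Malawi and Uganda sites". The documents do not support that. Section 5.1 fixes a first-to-last gain, which fits that phrase, and step 5 shows no established benefit from a slope. The game-level Table 3 cited in Sections 5.6.5 and 7.1.2 is not in the text reviewed and may say more.

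Finally, one might fear that a six-game total would be set against a five-game total. No passage plans a summed score.

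**Conclusion.** The point holds in two parts. The EF part of the Phase I dynamic endpoint cannot be formed as written: 0 of 300 trained children have a described session-1 EF score. It would be wrong to conclude that the dynamic endpoint as a whole fails, because the five core-game gains are unaffected. In addition, the predictive model combines a 12th-session score in 300 children with a repeat single-session score in 300 others, with no arm term and no named gain, so it does not isolate the quantity in the central hypothesis.

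The first part rests on reading session 1 as limited to the five games it names. The second rests on the covariates listed in Section 7.1.2; the missing Table 3 and figures could add detail. The power figures assume a simple linear model, and the comparison with Table 1 assumes that BPG behaves like a different game package in a different population. This should be corrected before analysis, but it does not threaten the study's feasibility.

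**What to change.** 1. Reconcile Sections 3.0, 5.1 and 5.6.6 on which games enter the Phase I gain. If the Phase 2 placement stands, limit the Phase I dynamic endpoint to the five core games and define the EF gain from Village Builder sessions 1 to 12 in Phase 2. State its analysis, including the comparison promised in Section 5.6.5, in Section 7.1.2.
2. In Section 7.1.2, enter the session-1 score and the session-12-minus-session-1 core-game gain as separate terms in BPG-trained children.
3. Analyse the wait-list intake-to-1-month change separately, labelled as retest change.
4. Optionally, prespecify the 12-session mean and slope as supplementary measures in trained children, after checking that scores share one scale: Section 5.1 gives session 1 as 50-60 minutes, Section 5.6.6 gives training sessions as 30-45 minutes. This is an addition, not a correction.

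The cost is wording in Sections 5.1, 5.6.6 and 7.1.2, with no new visits or data. The downside is that the gain analysis uses only the trained half, 300 of 600 children.
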